Presatovir exposures increased in an approximately dose-proportional manner over the dose range tested following single and multiple oral administrations under fasted conditions. Presatovir terminal half-lives ranged from 30 to 33 hours following single oral administration and approximately 36 hours following multiple oral administrations. Overall, the variability of the PK parameters was relatively low, with the majority of the PK parameters displaying CV% of 30% or lower. In addition, the food effect on presatovir PK following single or multiple oral administration has been evaluated. Following single administration of presatovir at 25, 50, or 75 mg, C_{max} under fed conditions decreased approximately 20% to 40% compared to fasted conditions, but this effect was less pronounced following once daily dosing at the higher dose (75 mg) around steady-state.

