1.2.4.3. Study GS-US-218-1010

Study GS-US-218-1010 was a Phase 1, partially-blinded, randomized, placebo- and positive-controlled study to evaluate the effect of presatovir on the QT/QTc interval in healthy subjects, with a lead-in, open-label, dose-ranging pilot phase to determine the suprathreshold dose of presatovir.

This study was a 2-stage study. Stage I was a lead-in, open-label, 3-cohort, single-dose ranging pilot study to determine the suprathreshold dose of presatovir. Stage II was a partially-blinded, randomized, placebo- and positive-controlled, 4-period, single-dose crossover study evaluating the effect of presatovir on the QT/QTc interval in healthy subjects. For Stage I and Stage II, a total of up to 24 (for 18 evaluable) and 48 (for 40 evaluable) subjects, respectively, were planned to be enrolled, with an approximately even distribution of healthy male and non-pregnant, non-lactating female subjects 18 to 45 years of age, inclusive.

In Stage I of the study, all 19 randomized subjects completed the study. In Stage II of the study, of 48 randomized subjects, 47 completed the study. One subject was withdrawn from the study due to investigator discretion. Demographic and baseline characteristics were balanced between Stage I and Stage II. Overall, subjects in the Safety Analysis Set (which combined Stage I and Stage II safety data) had a mean age of 34 years (range 20 to 45 years); most were predominantly white (80.6%), and of Hispanic/Latino ethnicity (95.5%), with slightly more males (59.7%) than females (40.3%). The mean (SD) BMI and estimated glomerular filtration rate (eGFR) values were 26.2 (2.62) kg/m² and 120.9 (15.34) mL/min, respectively.

Study GS-US-218-1010 showed that presatovir displayed approximately dose-proportional PK between 200 and 800 mg, with median terminal half-life ranging from 27 to 40 hours.

Presatovir, administered at doses of 200 and 800 mg, did not lead to changes in the QTc interval in healthy adults. Thus, this is a negative thorough QT study as defined by ICH guidance. Neither of the 2 doses of presatovir was associated with significant changes in ECG or wave morphology. There were no clinically relevant relationships between time-matched, baseline-adjusted, placebo-corrected QTcF or QTcI and plasma concentrations of presatovir.

Presatovir was generally well tolerated at doses of 200 and 800 mg.

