6.1.2.2. Randomization and Treatment Assessments (Day 1/Baseline)

After all Baseline assessments are complete, eligible subjects will be randomized via Interactive Voice/Web Response System (IWRS) and IMP will be administered.

- Randomization to presatovir or placebo will be based on a randomization schedule prepared by Gilead and/or designee before the start of the study. Subjects must continue to satisfy all inclusion/exclusion criteria at the time of randomization. Prior to randomization, eligible subjects will be stratified by the following:
 - Treatment of RSV infection (yes or no) with ribavirin (oral, intravenous, or aerosolized)
 - Use of palivizumab or IVIG (yes or no)

Treatment of current RSV infection with ribavirin will be defined as ≥ 1 dose of ribavirin (oral, intravenous, or aerosolized) prior to randomization or with written orders for the initiation of therapy at the time of randomization. Subjects will be randomized in a 2:1 ratio to receive IMP (presatovir) or placebo.

Subjects will receive a dose of 200-mg (4 x 50 mg tablets) of presatovir or PTM on Day 1/Baseline. All IMP will be administered orally or via a NG tube as described in Section 5.3 (Dosage and Administration of presatovir) above. Refer to Section 5.3 for IMP administration details.

The following procedures will be performed and documented on Day 1/Baseline after IMP administration:

- PK sampling at 2-4 hours post-dose
- Assessment of AEs and concomitant medications
- If applicable, clinical data collection for all standard of care cardiac-related tests performed during the study period (see Section 6.7.8)

6.2. Days 2 through 21 (± 24 hours window applies to each visit day)

Day 3, 5, 7, 9, 14, and 21 visits may be performed at home or in the local hospital/clinic. Visits are **NOT REQUIRED** on Day 2, 4, 6, 8, 10, 11, 12, 13, 15, 16, 17, 18, 19, and 20. (Refer to Appendix 2, Study Procedures Table)

On required in clinic/hospital/home subject visit days assessments should be performed in the following order whenever possible and documented:

- FLU-PRO questionnaire (Days 3, 5, 7, 9, 14, and 21)
- Oxygen requirement assessment (Days 3, 5, 7, 9, 14, and 21)

- Vital Signs (body temperature, heart rate, respiratory rate, and blood pressure) (Days 7, 14, 21)
- Negative local urine or serum pregnancy test for females of childbearing potential (Days 7 and 14)

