- PK blood draw (pre-dose on Days 7 and 14, and any time on Day 21). Subjects must have home visit blood draw completed prior to IMP administration on Days 7 and 14. Refer to Section 5.3 for guidance on IMP administration and relevant observation times.
- Blood draw for safety labs and plasma biomarkers (Days 7, 14, and 21)
- Nasal samples (2 total, 1 from each nostril) on Days 3, 5, 7, 9, 14, and 21
- PPD [REDACTED]
- PPD [REDACTED]
- IMP daily dosing (100 mg, Days 2 through 14); directly observed IMP administration (Day 7 and 14 only)
- Perform IMP accountability (Days 3, 5, 7, 9, 14, and 21)
- Assessment of AEs and concomitant medications (Days 3, 5, 7, 9, 14, and 21)
- Self administered handheld spirometry (these handheld spirometry measures will be collected specifically in the presence of study staff at Days 3, 5, 7, 9, 14, 21)
- If applicable, clinical data collection for all standard of care cardiac-related tests performed during the study period (see Section 6.7.8)
- If the subject is seen at the site for any reason (eg, hospitalization, clinic, or site visit) between Days 2 to 14, a blood draw for troponin measurement is required. Refer to Section 6.7.6 for additional information.
- If the subject is seen at the site for any reason (eg, hospitalization, clinic, or site visit) between Days 2 to 14, a 12-lead ECG is required. Refer to Section 6.7.7 for additional information.

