6.7.6. Safety Labs

When available, the most recent laboratory values (obtained ≤ 7 days prior to Screening) may be used for eligibility assessment, with the exception of RSV results and pregnancy testing. If an existing laboratory value is not available for eligibility assessment, the test will be performed using the local hospital laboratory. All testing of samples obtained after the Screening assessments (with the exception of an additional local troponin test on Day 1/Baseline and Day 28/End of Study) will be performed at a central laboratory selected by GSI.

Central laboratory testing of blood specimens for safety analysis will include CBC, sodium, potassium, chloride, CO₂, BUN, creatinine, glucose, AST and ALT, alkaline phosphatase, total bilirubin and CK on Days 1/Baseline, 7, and 14 (pre-dose) and on Days 21 and 28/End of Study.

Local laboratory testing of troponin will also be done at Day 1/Baseline and Day 28/End of Study for timely safety evaluation by the investigator. Local troponin testing will be done in accordance with the standard assay available at the site.

If the subject is seen at the site for any reason (eg, hospitalization, clinic, or site visit) between Days 2 to 14, a blood draw for troponin measurement is required. If the subject is at the site on more than 1 occasion between this timeframe, only 1 protocol-mandated measurement is required, but it should be obtained at the earliest feasible time and during the same study visit as the ECG measurement described below.

Samples will be sent to the local lab at the clinical site for troponin analysis using the laboratory-based assay specific to the local trial site (eg, troponin I or T). Point-of-care “rapid” troponin tests are not acceptable for protocol-mandated troponin testing. The baseline troponin test must be pre-dose. Troponin testing done for the purposes of patient care on the same day as a protocol-required test day may be used, provided the test is completed at the protocol-directed time and is a laboratory-based assay. Troponin results should be verified before the subject leaves the clinical site in case a troponin value is positive and further medical care is advised. Any additional troponin measures obtained for the purposes of patient care also require collection.

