6.7.7. Electrocardiogram (ECG)

As part of safety testing, at Day 1/Baseline a pre-dose 12-lead ECG will be performed on the clinic or local hospital equipment. A second 12-lead ECG will also be performed at Day 28/End of Study.

If the subject is seen at the site for any reason (eg, hospitalization, clinic, or site visit) between Days 2 to 14, a 12-lead ECG is required. If the subject is at the site on more than 1 occasion between this timeframe, only one protocol-mandated ECG measurement is required, but it should be obtained at the earliest feasible time and during the same study visit as the troponin measurement described above. ECG testing done for the purposes of patient care on the same day as a protocol-required test day may be used, provided the test is completed at the protocol-directed time. ECG results should be verified before the subject leaves the clinical site in case further medical care is advised. Any additional ECG measures obtained for the purposes of patient care also require collection.

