### **7.5. Electrocardiogram Assessment**

Number and percent of subjects with new ECG abnormalities at postbaseline visits including those assessments obtained for the purpose of standard of care will be summarized by treatments. Only subjects with baseline ECG assessments will be included in this analysis.

A shift table of the central ECG assessments at postbaseline visit including those assessments obtained for the purpose of standard of care compared with baseline values will be presented by treatment group using the following categories: normal, abnormal, no new abnormality, new abnormality, or missing. The number and percentage of subjects in each cross-classification group of the shift table will be presented. Subjects with a missing value at baseline or postbaseline will not be included in the denominator for percentage calculation. No formal statistical testing is planned.

A by-subject listing for ECG central assessments and ECG abnormalities, including those not required by the protocol (ie, standard of care), will be provided by subject ID number and visit in chronological order.

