### **7.6. Other Safety Measures**

A shift table of troponin results at postbaseline visit (including those obtained for the purposes of standard medical care) compared with baseline values will be presented by treatment group using the following categories: normal, abnormal, or missing. The number and percentage of subjects in each cross-classification group of the shift table will be presented. Subjects with a missing value at baseline or postbaseline will not be included in the denominator for percentage calculation. No formal statistical testing is planned.

If multiple troponin results exist for one visit due to multiple troponin assay tests performed, the results obtained from Troponin I test will be used for the analysis.

A by-subject listing for all troponin results, including those not required by the protocol (ie, standard of care), will be provided by subject ID number and visit in chronological order.

A data listing will be provided for subjects experiencing pregnancy during the study.

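### On-treatment ECG and troponin come only from subjects who attend the site, and the only post-baseline test scheduled for every completer falls about 9 half-lives after the last dose, so on-drug comparisons between arms risk selection bias and the SAP tables should be split by period

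*Protocol*

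**What the plan says.** - **Fixed tests.** Protocol 6.7.7 requires a pre-dose ECG on Day 1, then: "A second 12-lead ECG will also be performed at Day 28/End of Study". Protocol 6.7.6 fixes local troponin at the same two points. Early termination (6.5.2) adds both tests, but only for subjects who withdraw.
- **Conditional tests.** On Days 2 to 14, troponin is required "If the subject is seen at the site for any reason (eg, hospitalization, clinic, or site visit) between Days 2 to 14", and 6.7.7 words the ECG rule the same way. One of each is enough, at the first feasible site contact.
- **Where visits happen.** Protocol 6.2: "Day 3, 5, 7, 9, 14, and 21 visits may be performed at home or in the local hospital/clinic".
- **Half-life.** Protocol 1.2.4.1 gives "approximately 36 hours following multiple oral administrations". The QT study summary (1.2.4.3) reports dose-proportional kinetics "with median terminal half-life ranging from 27 to 40 hours".
- **ECG analysis.** SAP 7.5 will present the "Number and percent of subjects with new ECG abnormalities at postbaseline visits including those assessments obtained for the purpose of standard of care". The only stated condition for inclusion is a baseline ECG. A shift table follows.
- **Troponin analysis.** SAP 7.6 plans "A shift table of troponin results at postbaseline visit (including those obtained for the purposes of standard medical care) compared with baseline values". Both shift tables leave subjects with a missing value out of the percentage denominator.
- **Protocol rules for these data.** Protocol 8.6 sends treatment-free follow-up data to listings only. Protocol 8.7.3 promises ECG summaries by time point and against clinically relevant thresholds.

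**The concern.** Safety is a secondary objective, and cardiac events have their own search strategy in SAP Appendix 3. A subject followed at home can comply fully with the protocol and finish 14 days of dosing without an ECG or troponin on drug. That subject's only post-baseline result comes two weeks after the last dose, too late to show an effect that is present only while drug is present.

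Subjects who are tested on drug are those who came to the site. Some come for routine visits and some because they are ill. An effective antiviral could change how often subjects are admitted, so the tested subsets of the two arms may not be comparable.

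If the tables then mix Day 28 results, conditional on-drug results and clinically triggered results, a reader cannot see how many subjects per arm were examined on drug. An absence of findings could be taken as reassurance it does not give. The one scheduled DMC safety review was cancelled (SAP 2.1 and 7.7), so the final tables carry more weight.

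**Working it through.** The documents state no number of half-lives and no precision target for cardiac safety, so there is no plan figure to reproduce.

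**1. Drug left at Day 28.** Inputs: last dose on Day 14 (Protocol 3.4, 5.3); final visit on Day 28 with a window of +2 days (6.3). Elapsed time is (28 − 14) × 24 = 336 h. Half-lives elapsed = 336 / t½; fraction left = 0.5^(half-lives).

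| t½ | Half-lives by Day 28 | Fraction left |
|---|---|---|
| 27 h | 336/27 = 12.4 | 0.02% |
| 36 h | 336/36 = 9.3 | 0.16% |
| 40 h | 336/40 = 8.4 | 0.30% |
| 36 h, visit on Day 30 | 384/36 = 10.7 | 0.06% |

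Protocol 5.4 allows CYP3A inhibitors, and a strong one raised AUC by about 122% and Cmax by 13% (1.2.4.6). Assumption: the half-life lengthens by a factor between 2.22/1.13 = 1.96 and 2.22, giving about 71 to 80 h. Then 336 h is 4.8 to 4.2 half-lives, with 3.7% to 5.4% left. Day 28 is essentially off drug in every case.

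**2. How many are tested on drug.** About 60 × 2/3 = 40 subjects receive presatovir. The documents give no attendance figures, so the range is shown. If a fraction f attends, n = 40f are tested, and the chance of seeing at least one finding at an assumed true rate of 5% is 1 − 0.95^n.

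| f | n tested | Chance of at least one finding |
|---|---|---|
| 25% | 10 | 40% |
| 50% | 20 | 64% |
| 75% | 30 | 79% |
| 100% | 40 | 87% |

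**3. Effect of the denominator in the new-abnormality count.** Because SAP 7.5 asks only for a baseline ECG, a subject tested only on Day 28 stays in the denominator. If such subjects have no findings, the reported rate is f times the rate among those tested on drug: a quarter of it at f = 25%, half at 50%, three quarters at 75%.

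**4. The passages side by side.**
- Protocol 8.6 tabulates the treatment period only. SAP 7.5 and 7.6 tabulate post-baseline results without limiting them to it.
- Protocol 8.7.3 has ECG by time point and against thresholds. SAP 7.5 mentions neither, and SAP 7.7, which records changes from the protocol's safety analyses, lists only the cancelled DMC meeting.
- The SAP table list has one ECG shift table, one new-abnormality table and one troponin shift table. None is titled by period or visit.
- SAP 3.8.2 assigns unscheduled results to no visit, and moves early-termination results to the next visit at which that test was scheduled. For ECG and troponin after baseline that is Day 28, so an early-termination ECG taken on drug would carry the Day 28 label.

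**The case against.** **Other cardiac data exist.** A reader might infer that the trial cannot assess cardiac safety on drug at all. The documents do not support that. Adverse events are assessed at every visit from Day 3, and CK, heart rate and blood pressure are measured on Days 7 and 14, in all subjects and under blind. Cardiac adverse events are analysed by arm in the whole Safety Analysis Set (SAP 7.1.7). This stands, and limits the point to ECG and troponin, mainly silent changes. One qualification: the Appendix 3 search also draws on ECG and cardiac-muscle test terms, so part of that analysis inherits the selective testing.

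**Direction of bias.** A reader might also infer that the bias favours presatovir, because fewer admissions would mean fewer tests. It could equally run the other way: if the drug caused cardiac symptoms, presatovir subjects would attend and be tested more. Attendance for any reason also includes routine visits, so the subset is not purely one of ill subjects. Without attendance by arm, neither size nor direction can be stated.

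**The tables may be by visit.** SAP 3.8.2 uses nominal visits for by-visit summaries, SAP 7.6 resolves multiple troponin results within one visit, and the shift tables have a missing category. That is a fair reading of the shift tables. It does not cover the new-abnormality count, and it leaves open where unscheduled standard-of-care results go.

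**Treatment period may run to Day 28.** Protocol 8.7.1 and 8.7.2 count adverse events and laboratory abnormalities up to Day 28, so 8.6 might be read the same way. Then the term needs defining, because 8.6 also names a treatment-free follow-up period.

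**Earlier ECG evidence is reassuring.** The QT study was negative at 200 and 800 mg, and multiple-dose ECGs in the first-in-human study showed no clinically significant change. This makes site-contingent ECGs a defensible burden trade-off. Those subjects were healthy, however; the QT study used single doses, and the multiple-dose regimen reached 75 mg daily for 7 days.

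**Conclusion.** The point holds for ECG and troponin. The only post-baseline test scheduled for every completer is about 9 half-lives after the last dose (8.4 to 12.4 over the stated half-lives; about 4 to 5 if a strong CYP3A inhibitor roughly doubles the half-life, which is an assumption). Protocol-required on-drug tests come from a subset defined after randomisation. Between-arm comparisons of on-drug ECG and troponin findings are therefore open to selection bias of unknown size and direction, and the SAP plans no count that would show how far the arms differ in testing.

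The SAP wording adds an avoidable problem: no stated split by period, and a new-abnormality denominator that includes subjects never tested on drug. Protocol 8.6 and 8.7.3 and SAP 7.5 and 7.6 must be reconciled. The half-life arithmetic rests on documented values; the attendance shares and the 5% rate are illustrations. This is an inexpensive improvement to reporting, not a finding that the trial's safety assessment fails.

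**What to change.** Revise SAP 7.5 and 7.6 and the table list as follows.

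1. Present ECG and troponin separately for an on-treatment period and for Day 28. Define the periods by date relative to the last dose, not by visit label, and pre-specify and justify the end of the on-treatment period, for example as a stated number of half-lives after the last dose.
2. Report the number tested per arm in each period and use it as the denominator.
3. Show protocol-mandated tests and standard-of-care tests separately.
4. State in a footnote that on-treatment results come from subjects who attended the site.
5. Reconcile this with Protocol 8.6 and 8.7.3, and record any remaining departure in SAP 7.7.

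The cost is table programming, a few more tables and smaller on-treatment denominators. No new data are needed, which matters because SAP 7.7 indicates that enrolment ran too fast for a DMC review before dosing ended.

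Adding troponin to the Day 7 and Day 14 blood draws might seem the natural remedy, but it is not proposed. Those samples go to a central laboratory and may be drawn at home. Troponin is each site's own laboratory assay, with the result checked before the subject leaves. The addition would set a central result against a local baseline and would supply no ECG.

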6.7.7. Electrocardiogram (ECG)

As part of safety testing, at Day 1/Baseline a pre-dose 12-lead ECG will be performed on the clinic or local hospital equipment. A second 12-lead ECG will also be performed at Day 28/End of Study.

If the subject is seen at the site for any reason (eg, hospitalization, clinic, or site visit) between Days 2 to 14, a 12-lead ECG is required. If the subject is at the site on more than 1 occasion between this timeframe, only one protocol-mandated ECG measurement is required, but it should be obtained at the earliest feasible time and during the same study visit as the troponin measurement described above. ECG testing done for the purposes of patient care on the same day as a protocol-required test day may be used, provided the test is completed at the protocol-directed time. ECG results should be verified before the subject leaves the clinical site in case further medical care is advised. Any additional ECG measures obtained for the purposes of patient care also require collection.

6.7.8. Collection of Standard of Care Clinical Data for Central Review

During the course of the 28-day study, it is anticipated that Investigators may perform an array of tests related to respiratory infection testing or related to care of the transplanted lung(s) as part of standard of medical care.

If such assessments are performed, the following data will be collected:

- The results of all spirometry and any other pulmonary function data done (in addition to study-mandated testing)
- The results of all BALF analyses, including cell profiles and microbiologic studies

- The results of all microbiological data reports on respiratory (lung tissue, sputum, BAL, nasal or nasopharyngeal fluid/washes) and blood culture samples
- Radiological images of the chest (chest radiographs and CT scans only) and the associated radiology interpretation reports
- Electronic copies of all lung pathology images, and the associated pathology interpretation reports
- Whether the subject died (yes or no), date of death if appropriate, and the results of any autopsy reports

Additionally, throughout the study period (Day 1/Baseline through Day 28/End of Study) if any cardiac monitoring procedure is performed as part of standard clinical care, or as part of AE/SAE evaluation and/or follow-up, these results will be collected, including but not limited to the following standard of care procedures:

- ECG tracings and results report of any ECG performed
- Cardiac enzyme testing (eg, all troponin results, CK-MB, etc)
- Cardiac stress testing
- Echocardiographic imaging (resting and stress testing)
- Cardiac perfusion scans
- Cardiac MRIs
- Any additional procedure used to evaluate cardiac conditions

